9.2.5. Postoperative 3 Months

All routine, usual standard of care postoperative measures should be undertaken. In addition, the subject will undergo a manifest refraction, VA, and lens orientation testing and complete the QUVID and IOLSAT questionnaires (Section 9.3). Any device deficiencies or adverse events will be monitored.

9.2.6. Exit Procedures

In the event of premature exit from the study, all study related examinations should be completed where possible. The Exit CRF should be completed, noting that the subject did not complete the study and the reason for premature study exit. If no premature exit from the study occurs, the Exit CRF should be completed at the end of Visit 5 (Postoperative 3 Months).

9.3. Study Methods and Measurements

All routine testing and basic eye examinations should be carried out at each study visit. Abnormalities should be recorded in the CRF “Comment” section. Specific study examination procedures are outlined below.

9.3.1. Manifest Refraction

Perform a manifest refraction with a high contrast logMAR chart under photopic lighting conditions ($>85 \text{ cd/m}^2$). Document refraction results with sphere, cylinder and axis readings. If uncorrected visual acuity is not improved by

manifest refraction, use zero for sphere and cylinder and draw a line through the blank for the axis.

Note: Each subject should be manually refracted to his/her best correction by an ophthalmologist, optometrist, or a skilled technician using a phoropter or trial lenses.

9.3.2. Visual Acuity (VA)

Visual acuity will be measured using the M&S Technologies Clinical Trial System. All relevant data will be recorded internally.

It is sufficient to record the uncorrected VA at distance only for the 1-day visit.

All other visual acuity testing is performed binocularly. Postoperatively conduct testing uncorrected at all visits. In addition, conduct testing with the manifest distance refraction in place at 1 month and 3 months post-operatively.

Distance VA

Measure distance VA at a distance of 6 m.

Intermediate VA

Measure intermediate VA at a distance of 60 cm.

Near VA

Measure near VA at a distance of 40 cm or 33 cm.

9.3.3 Questionnaires

The patient satisfaction (IOLSAT) questionnaire and the visual disturbance (QUVID) questionnaire, related to quality of vision, will be administered to subjects at the 1 and 3-month visits. The administrator should ensure the subjects understand the nature of the questions but should not interpret them for the subject.

9.4. Unscheduled Visits

Unscheduled exams may be conducted at the discretion of the Investigator with all relevant information from the exam recorded in the source documents and on the Unscheduled Visit pages within the CRF booklet.

9.5. Discontinued Subjects

Discontinued subjects are those who do not have an exit visit or who come into the office to be exited prior to the scheduled final study visit. Subjects may be discontinued from the study at any time if, in the opinion of the investigator, their continued participation in the study poses a risk to their health. The reasons for discontinuation include:

- a. Adverse event;

- b. Lost to follow-up;
- c. Subject decision unrelated to an adverse event;
- d. Protocol violation;
- e. Treatment failure;
- f. Other.

To ensure the safety of all subjects who discontinue prior to Visit 5, investigators should assess each subject and, if necessary, advise them of any therapies and/or medical procedures that might be needed to maintain their health. Any changes in medical health and/or use of concomitant medications should also be captured.

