3. GENERAL INFORMATION

Objective	To evaluate visual outcomes and quality of vision following bilateral implantation of the Clareon PanOptix intraocular lens (IOL) targeted for emmetropia.
	The hypothesis is that the Clareon™ PanOptix™ Trifocal IOL will provide good overall quality of vision and visual outcomes.
Test Article(s)	The Clareon™ PanOptix™ Trifocal (toric and non-toric models)
Control Article(s)	None.
Sample size	70 eyes of 35 subjects
Study Population	Subjects \geq 40 years of age presenting for cataract surgery who are interested in reducing their dependence on spectacles at all distances, and who are appropriate candidates for trifocal lens implantation.
Number of sites	One
Study Design	Prospective, non-randomized, single-arm study.
Masking	None
Variables	Primary: Binocular distance-corrected near (40 cm) visual acuity), 1 and 3-months postop Secondary: 
• Bilateral visual acuity outcomes (uncorrected and best-distance-corrected) at distance (6m), intermediate (60 cm), and near (40 cm), 1 and 3-months postop• Manifest refraction (residual spherical equivalent refraction, residual sphere, and residual astigmatism), 1 and 3-months postop• Binocular, distance corrected defocus curve at 3 month post-operatively, using standard parameters: (+1.00 to -3.00 in 0.50D except +0.50 to -0.50 in 0.25D).• Questionnaire for visual disturbance scores (QUVID)

- Patient satisfaction questionnaire scores (IOLSAT)

Exploratory:

- Binocular DCNVA at 33cm, 1 and 3-months post-operatively.

Duration / Follow-up Preoperative to 3 months postoperative

The study will be registered with clinicaltrials.gov.

The study will be conducted in compliance with the protocol, GCP and applicable regulatory requirements

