8. STUDY DESIGN

8.1. Study Design

This study is a single-arm unmasked clinical evaluation study of binocular distance-corrected near (40 cm) visual acuity after successful bilateral cataract surgery. Subjects will be assessed pre-operatively, operatively and at 1 day, 1 month and 3 months post-operatively. Clinical evaluations will include administration of a visual disturbance questionnaire (QUVID), and a satisfaction questionnaire (IOLSAT), as well as measurement of bilateral visual acuity and manifest refraction.

The primary outcome measure will be the binocular distance-corrected near (40 cm) visual acuity at 1 and 3 months postoperative.

Secondary outcome measures are as follows:

- Bilateral visual acuity outcomes (uncorrected and best-distance-corrected) at distance (6m), intermediate (60 cm), and near (40 cm), 1 and 3-months postop
- Manifest refraction (residual spherical equivalent refraction, residual sphere, and residual astigmatism), 1 and 3-months postop
- Binocular, distance corrected defocus curve at 3 month post-operatively, using standard parameters: (+1.00 to -3.00 in 0.50D except +0.50 to -0.50 in 0.25D).
- Questionnaire for visual disturbance scores (QUVID)
- Patient satisfaction questionnaire scores (IOLSAT)

Exploratory outcome measures are as follows:

- Binocular DCNVA at 33cm, 1 and 3-months post-operatively

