10. ANALYSIS PLAN

10.1. Analysis Data Sets

All subjects who are enrolled in the study will be evaluated for safety. Efficacy analyses will be performed based on data from those eyes where uncomplicated cataract surgery with PanOptix IOL implantation was completed.

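### An undefined treatment-failure exit (9.5), combined with summaries restricted to completers (10.2), can drop poor results from a single-arm estimate of good vision

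*Combined protocol and SAP*

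**What the plan says.** Section 3 sets the hypothesis that the lens "will provide good overall quality of vision and visual outcomes". The study has one arm, one site, no control and no masking. Section 8.1 states: "The primary outcome measure will be the binocular distance-corrected near (40 cm) visual acuity at 1 and 3 months postoperative".

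Section 9.5 counts a subject as discontinued if there is no exit visit, or if the exit comes before the final scheduled visit. It lets the investigator discontinue a subject "if, in the opinion of the investigator, their continued participation in the study poses a risk to their health". A list of six reasons follows. The fifth is "e. Treatment failure", and no section defines it. Adverse event, loss to follow-up, the subject's own decision and protocol violation are separate items.

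Section 9.2.6 provides for early leavers: "In the event of premature exit from the study, all study related examinations should be completed where possible". The reason goes on the Exit CRF.

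Two analysis populations are given. Section 10.1: "Efficacy analyses will be performed based on data from those eyes where uncomplicated cataract surgery with PanOptix IOL implantation was completed". Section 10.2 says its summaries cover the eyes that complete the study, and 18.1 defines completion as having completed Visit 5. Section 18.3 adds that patients terminated for a severe, possibly related adverse event count as having completed. Nothing comparable covers treatment failure. No section gives a rule for missing values.

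**The concern.** The treatment under study is a pair of lenses placed at surgery. Afterwards the study measures acuity, refraction, lens orientation, the defocus curve and questionnaires, and monitors adverse events. Surgery that is not completed successfully is handled separately in 9.2.2. One natural meaning left for treatment failure is therefore an unsatisfactory result with the lens. On that meaning, the reason for leaving is the outcome itself, and the loss is informative by construction.

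The result is a descriptive estimate with no comparator. Losing poor results improves the mean and shortens the tail, and no control arm shares the distortion. Restricting 10.2 to completers makes this worse, because values already collected from such a subject would also be set aside.

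**Working it through.** **1. The plan's own figure.** Section 11 needs 32 subjects, allows 10% dropout and enrols 35. Check: 32 / 0.90 = 35.6, which rounds up to 36; 35 × 0.90 = 31.5, about 32. The stated 35 agrees to within one subject. The room for loss is 35 − 32 = 3 subjects (3/35 = 8.6%). The plan gives no SD, effect size or power, so nothing else can be reproduced.

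**2. What happens to the data.** Take a subject who has Visit 4 and then exits as a treatment failure before Visit 5.

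| Value | Collected? | 10.1 set | 10.2 read literally |
|---|---|---|---|
| 1-month binocular distance-corrected near acuity (DCNVA) | Yes | Kept | Dropped |
| Exit examination (9.2.6) | Where possible | Eligible, but assigned to no visit | Dropped |
| 3-month DCNVA | No | Missing, no rule | Missing, no rule |
| Defocus curve (Visit 5 only) | Only if done at exit | Eligible if done, assigned to no visit | Dropped |
| Postoperative IOLSAT and QUVID | At 1 month per 9.2.4 and 9.3.3; Table 15.1 shows Visit 5 only | Kept if collected | Dropped |

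The 3-month window in Table 9.2-1 is 90 ± 20 days, so an exit examination before day 70 is not a 3-month value. A subject who exits before Visit 4 has no 1-month value either.

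**3. Size for the mean (assumed inputs).** Let k of 35 subjects leave with a mean DCNVA d logMAR worse than the completers' mean m.

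All-subject mean = [(35 − k)m + k(m + d)] / 35 = m + kd/35, so the completer mean is too favourable by kd/35.

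| | d = 0.1 | d = 0.2 | d = 0.3 |
|---|---|---|---|
| k = 1 | 0.003 | 0.006 | 0.009 |
| k = 2 | 0.006 | 0.011 | 0.017 |
| k = 3 | 0.009 | 0.017 | 0.026 |

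At 0.02 logMAR per letter, the largest entry is 0.0257 / 0.02 = 1.3 letters. As an example, with completers at 0.10 and three exits at 0.40: (32 × 0.10 + 3 × 0.40) / 35 = 4.4 / 35 = 0.126, against a reported 0.100. If all completers are better than 0.40, the 0.40 also vanishes from the planned maximum.

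**4. Extreme case.** Suppose the three worst of 35 normally distributed values are lost (200,000 simulated samples). The mean shifts by 0.164 SD and the reported SD falls to 0.867 of its full-sample value, about 13% lower. For an assumed SD of 0.08 to 0.15 logMAR, the shift in the mean is 0.013 to 0.025 logMAR.

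**The case against.** A reader might infer that 9.5 is a rule for removing subjects whose lens works badly. The text does not support that. The power given to the investigator is conditional on a risk to health, and poor acuity is not named. The list also contains loss to follow-up and the subject's own decision, which no investigator can invoke. It reads at least as naturally as a set of codes for the Exit CRF. Treatment failure could mean removal or exchange of the lens, after which acuity no longer describes this lens. All of this stands. It reduces the point from a stated rule to an undefined term whose use is left to an unmasked investigator.

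A reader might also infer that the primary result of such a subject is lost beyond recovery. That goes too far. The primary outcome is measured at 1 and 3 months, so a subject who leaves after Visit 4 has one primary value. Section 9.2.6 asks for an exit examination, and 10.1 would keep the eyes. These protections are real but partial: the examination is only where possible, an early value is not a 3-month value, and 10.2 as written discards both.

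The mismatch between 10.1 and 10.2 affects every early exit, not only this one. That is true. Treatment failure is the code for which the loss is most likely to depend on the outcome. Deleting the code alone would not help, because the same exits would be recorded as subject decision or other.

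Finally, the 10% allowance is for dropout of all kinds, so giving all three spare subjects to treatment failure is an upper-end illustration.

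**Conclusion.** The point holds as a combination of three things: an undefined outcome-like exit reason in 9.5, a completer restriction in 10.2 that conflicts with 10.1, and no rule for missing values. Together they leave a path by which poor results drop out of an uncontrolled estimate, in the direction that favours the hypothesis.

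The effect on the mean is modest: at most about 0.026 logMAR (1.3 letters) over the range shown, with three exits of 35 and a deficit of 0.3 logMAR. The effect on the SD and the maximum is more visible. The number of such exits, their deficit and the SD are assumptions; the documents give none of them. The plan has no responder threshold, so the effect cannot be restated as a success rate without adding one. The documents do not show that the sponsor intends to exit poor performers. This is worth correcting, but it does not undermine the study.

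**What to change.** 1. **Section 9.5.** State that poor visual performance alone is an outcome and does not end study measurement. Leave the existing safety, administrative and voluntary exits in 9.5, 18.2 and 18.3 as they are, and reconcile those passages with each other, including how 18.3's deemed completion fits with 18.1. The change concerns data collection only and does not alter who may leave for clinical reasons.
2. **Exit code.** Keep treatment failure only as a defined exit-reason code, for example removal or exchange of the lens.
3. **Section 10.2.** Replace the completer restriction with the 10.1 implanted set, using all available values at each visit. Since the primary outcome is binocular, say how that set, defined by eye, translates to subjects.
4. **Reporting.** Alongside the primary table, list every implanted subject who exits early, with the reason and the last acuity (the last one before removal, if the lens was removed or exchanged).

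The cost is a few sentences and one short listing, with no added visits or tests. Results may look slightly less favourable.

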10. ANALYSIS PLAN

10.1. Analysis Data Sets

All subjects who are enrolled in the study will be evaluated for safety. Efficacy analyses will be performed based on data from those eyes where uncomplicated cataract surgery with PanOptix IOL implantation was completed.

10.2. Statistical Methodology

A summary of the data will be prepared for all measurement time points. Summaries of the changes observed between the 1-month and 3-month post-operative visits will also be summarized.

For variables measured on a continuous scale, these summaries will include the sample size, as well as the mean, standard deviation, median, minimum, and maximum. For variables measured on a categorical scale, summaries will provide the number and percentage of subjects who provided each score (or change in scores). These summaries will be provided for all eyes completing the study.

10.2.1. Within-treatment Changes

For variables measured on a continuous scale, the statistical significance of within-treatment changes between time points will be investigated using paired t-tests. For variables measured on an ordinal categorical scale, the Wilcoxon signed-rank test will be employed.

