9.2. Visits and Examinations

Subjects will participate in seven study visits, one eye per visit for bilateral surgery. Visits will include an uptake visit, two operative visits, and 4 total postoperative visits (Visit numbers 1-5 below). The visit schedule, complete with window and associated

CRF forms, are displayed in Table 9.2-1. Details of each study visit, including testing to be conducted, are provided below.

Table 9.2-1. Visit Schedule

Visit Number	Visit Name	Visit Window	CRF Number
1	Preoperative	-30 to 0 days from surgery	1
2,2a	Operative	0 from surgery	2,2a
3,3a	1 Day Postoperative	1-2 days postoperative*	3,3a
4	1 Month Postoperative	30 (± 10) days postoperative**	4
5	3 Months Postoperative	90 (± 20) days postoperative**	5

* relative to the operative eye

** relative to the date the last eye is operated on

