15. STANDARD EVALUATION PROCEDURES

Table 15.1. Proposed Visits and Study Assessments
(visits are by patient, with both eyes tested)

Activity	Pre-operative	Operative	Postoperative		
	Visit 1	Visit 2	Visit 3	Visit 4	Visit 5
			1 Day	1 Month	3 Months
Informed Consent	X				
Demographics	X				
General Information: Medical History		X			
Surgery			X		
Manifest refraction	X			X	X
Monocular uncorrected distance VA (6m)	X		X	X	X
Monocular corrected distance VA (6m)	X			X	X
Binocular uncorrected and best- corrected distance VA (6m)				X	X
Binocular uncorrected and best distance-corrected intermediate VA (60cm)				X	X
Binocular uncorrected and best distance-corrected near VA (40cm & 33cm)				X	X
Binocular Distance Corrected Defocus Curve (6m)					X
IOLSAT Patient Satisfaction Survey	X				X
QUVID Visual Disturbance questionnaire	X				X
Monitor for Adverse Events and Device Deficiencies		X	X	X	X
Complete Exit Form ¹					X

¹ Complete Exit Form upon termination of subject participation, or at Visit 5, whichever occurs first.

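### Read with the eye-based efficacy set, the paired t-tests on 1-to-3-month refraction change would treat about 64 fellow eyes of 32 subjects as independent (minor; one secondary outcome)

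*Combined protocol and SAP*

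**What the plan says.** Section 10.1 sets the efficacy population by eye: "Efficacy analyses will be performed based on data from those eyes where uncomplicated cataract surgery with PanOptix IOL implantation was completed". Section 10.2 plans descriptive summaries at every time point and adds: "Summaries of the changes observed between the 1-month and 3-month post-operative visits will also be summarized". It closes with: "These summaries will be provided for all eyes completing the study". Section 10.2.1 then says, for continuous variables, that "the statistical significance of within-treatment changes between time points will be investigated using paired t-tests". Section 10.3 sets alpha at 0.05 without stating sidedness.

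The listed outcome with a value for each eye is the secondary outcome in section 8.1, "Manifest refraction (residual spherical equivalent refraction, residual sphere, and residual astigmatism), 1 and 3-months postop". Section 9.3.1 records it as sphere, cylinder and axis. Section 7.1 requires both eyes of a subject to be enrolled, and the note to Table 15.1 reads "visits are by patient, with both eyes tested". Section 11 expects 32 subjects (64 eyes) out of 35 (70 eyes) enrolled.

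The plan does not mention averaging over eyes, choosing one eye per subject, a mixed model, GEE or cluster-robust standard errors.

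**The concern.** The pairing in a paired t-test links the 1-month and 3-month values of the same eye. It does nothing about the link between the two eyes of one subject. If fellow eyes tend to change in the same direction, 64 eye-level changes carry less information than 64 independent ones. The standard error is then too small and the p-value too low.

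At stake is whether a shift in sphere, spherical equivalent or astigmatism between the two visits is called significant more often than the stated 5% allows. Section 12 foresees publication, so such a p-value could be reported at face value. The mean change itself is the same either way when both eyes of every subject contribute.

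**Working it through.** **Inputs from the documents.** 32 evaluable subjects and 64 eyes; 35 subjects and 70 eyes enrolled (section 11); alpha 0.05 (section 10.3), taken as two-sided.

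**The plan's own figure.** 32 × 2 = 64 and 35 × 2 = 70. With 10% dropout, 35 × 0.9 = 31.5, about 32 subjects. The count of about 64 eyes is therefore the plan's own. Section 11 gives no power, effect size or SD, so there is no power figure to reproduce.

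**Assumed input.** The correlation rho between the two eyes' 1-to-3-month changes is not in the documents. It is varied from 0 to 0.7. What matters is the correlation of the change, not of refraction itself.

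**Formula.** Take n subjects with two eyes each, per-eye SD of change σ, and no true change.

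- True variance of the mean over 2n eyes: σ²(1 + rho)/(2n).
- Variance the eye-level test uses: s²/(2n). The expected value of s² is σ²[(1 + rho)(n − 1) + (1 − rho)n]/(2n − 1). For n = 32 this is σ²(63 − rho)/63, almost exactly σ².
- The standard error is therefore too small by a factor of about 1/√(1 + rho), which is 0.82 at rho 0.5. The effective number of eyes is 64/(1 + rho), which is 42.7 at rho 0.5.
- Approximate type I error: 2[1 − Φ(1.96/√(1 + rho))]. At rho 0.5, 1.96/1.225 = 1.60, giving about 11%.

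**Results.** The first row averages the rejection probability of the t-test (63 df) over 4,000,000 draws of the variance. The second is a direct simulation of 400,000 trials per setting in which 4 of the 32 subjects contribute one eye (60 eyes), which the by-eye rule in 10.1 allows.

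| | rho 0 | 0.1 | 0.3 | 0.5 | 0.7 |
|---|---|---|---|---|---|
| Type I error, eye-level test, 64 eyes | 5.0% | 6.2% | 8.6% | 11.0% | 13.5% |
| Same, 4 subjects with one eye | 5.0% | 6.0% | 8.3% | 10.6% | 13.0% |
| Subject-level p when eye-level p = 0.050 | 0.055 | 0.066 | 0.090 | 0.113 | 0.136 |

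The third row refers t(0.975; 63 df)/√(1 + rho) to 31 df. With 35 subjects the first row changes by less than 0.1 percentage point.

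The t-test on each subject's mean change stayed between 4.9% and 5.1% in all these settings. A random-intercept model on balanced data with n − 1 df gave 4.0%, 4.5%, 5.0%, 5.0% and 4.9% at the five values of rho, so it is slightly conservative at low rho and never inflated.

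**The case against.** The strongest objection is that the eye-level test is inferred. Section 10.2.1 is the only place that specifies tests, and it names no unit. Section 10.1 can be read as a filter on which data qualify. It covers all efficacy analyses, including binocular outcomes with one value per subject, so it cannot literally set the unit of every test. Section 10.2 counts subjects for categorical scores, so its wording is loose. This stands: a reader might infer that the plan instructs an eye-level test, and it does not. But the eye is the only unit given for the efficacy set. If the subject was meant, the plan still does not say how two refractions become one value, so the clarification is needed on either reading.

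Second, the size depends on an assumed rho. This also stands: at rho 0 there is no inflation, and the figures of 11% and above need rho of 0.5 or more, which nothing in the text establishes. A reader might infer a positive rho from both eyes being refracted at one visit, perhaps by one examiner who differs between visits. The documents do not say that examiners change or that one examiner refracts both eyes. A shift common to all subjects would in any case bias the mean, and averaging eyes would not remove it. No such argument is relied on here.

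Third, the consequence is small in a largely descriptive single-arm study. This stands and sets the weight given to the point.

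**Conclusion.** The point holds as a minor one. The plan leaves the unit of its tests unstated, its efficacy set and summaries are by eye, and nothing accounts for two eyes per subject. On the reading this invites, the type I error for refraction change is 5.0% to 13.5% over rho 0 to 0.7. That range assumes 32 subjects, two-sided testing, normally distributed changes, independent subjects and equal variance in the two eyes.

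The scope is one secondary outcome with three variables. Monocular distance acuity would join it if analysed: Table 15.1 schedules it at 1 and 3 months, although section 9.3.2 describes acuity testing beyond the 1-day visit as binocular. A reader might infer that the primary result is also affected. It is not: binocular distance-corrected near acuity, the other binocular acuities, the defocus curve and the questionnaires have one value per subject. No success criterion depends on the refraction p-values.

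**What to change.** In section 10.2.1, name the unit of each test. State that per-eye variables (manifest refraction, and monocular distance acuity from Table 15.1 if it is analysed) are tested with a paired t-test on each subject's mean change over the qualifying eyes. A linear mixed model for change with a random subject effect and subject-based degrees of freedom is an acceptable alternative, slightly conservative at low rho. In section 10.2, require the number of eyes and the number of subjects in every table of a per-eye variable.

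The cost is one sentence in each section, with no new data or visits. P-values for refraction change become somewhat larger. The standardised change detectable with 80% power is 0.511 for 32 independent values and 0.356 for 64. In per-eye SDs, the subject-mean test detects 0.511 × √((1 + rho)/2): 0.36, 0.41, 0.44 and 0.47 at rho 0, 0.3, 0.5 and 0.7, against 0.36 if 64 eyes are taken as independent. At rho 0 almost nothing is lost. At higher rho the 0.36 is not a real advantage, because it comes with the inflated error rate.
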